2.2.3 Exploratory Endpoints

Exploratory analysis not necessarily identified in this SAP may be performed to support the clinical development program. Any post-hoc or unplanned analysis not identified in this SAP performed will be clearly identified in the respective CSR.

3 STUDY METHODS AND ENDPOINTS

3.1 Overall Study Design and Plan

This is a randomized (1:1), placebo-controlled, double-blind, parallel-group study of MN-166 (ibudilast) in hospitalized COVID-19 subjects at risk for developing ARDS receiving standard of care including anticoagulation. Approximately 40 participants are planned to be enrolled. The study will consist of a Screening Phase followed by a 7-days Double-blind Treatment (DBT) and Follow-up Phase. Following the Screening Phase, if the subject meets eligibility criteria, subject will be administered treatment with MN-166 (ibudilast) or placebo. Subjects will receive ibudilast 100 mg/d (50 mg b.i.d) or placebo every day for 7 days. The Follow-up phase is consisted of three visits: Day 14, Day 28, and Day 60 (subjects enrolled under amendment 4 only) post-baseline visit.

Subjects who are discharged prior to Day 7 will be given the remainder of their study medication to be taken at home and a pulse oximeter supplied by the sponsor to measure their O₂ levels once daily until Study Day 14.

Eligible participants will consist of males and females ranging in age from 21 to 80 years old, inclusive, who have SARS-CoV-2 infection confirmed by WHO criteria, chest abnormalities consistent with COVID-19 pneumonia, SpO₂ ≤92% on room air, ≥24 BPM, and/or requirement of supplemental O₂.

Overall study design and plan is described in detail in Protocol Section 11.

3.2 Selection of Study Population

Inclusion and exclusion criteria are described in detail in Final Protocol Sections 12.2 and 12.3.

Confidential

3.3 Method of Treatment Assignment and Randomization

During the Double-blind Treatment Phase, randomization occurred in a 1:1 ratio (MN-166: Placebo). The randomization scheme was generated by an independent statistician and sent to each site's unblinded pharmacist in a password protected file.

3.4 Treatment Masking (Blinding)

Participants and all personnel involved with the conduct and interpretation of the study, including the investigators, site personnel, and sponsor staff will be blinded to the treatment codes. Randomization data will be kept strictly confidential, filed securely by an appropriate group with the sponsor and accessible only to authorized persons (e.g., unblinded pharmacist) until the database is locked

To ensure that treatment allocation remains concealed to both staff and participants, the following measures will be taken:

- Active drug and placebo will be identical in appearance
- Drug supplies to investigational pharmacy will be coded

4 SEQUENCE OF PLANNED ANALYSIS

4.1 Interim Analysis

There are no planned interim analyses for this study.

4.2 Data Monitoring Committee Meetings

Not applicable.

5 SAMPLE SIZE DETERMINATION

No prior data are available on which to base assumptions for sample size/power considerations. The results of this pilot study will be used to design future studies, and the sample size of approximately 40 participants is deemed to be appropriate for this purpose.

6 ANALYSIS POPULATIONS

The following analysis populations are planned for the studies:

- **Full Analysis Set (FAS)** will include all randomized subjects.
- **Safety Analysis Set (SAS)** will include all randomized subjects who received at least one dose of study drug and had at least one post-dose safety assessment.
- **Per Protocol Analysis (PP):** will consist of the FAS subjects excluding those with major protocol violations.

Confidential

- **Pharmacokinetic Population (PK):** will consist of the subjects for which PK collection was performed. Eight subjects are anticipated to participate in PK sample collection.

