7.0 SCHEDULE OF ASSESSMENTS

Table 1 Schedule of Assessments

Phase	Screening	Double-Blind Treatment Phase ^{e,g}							Follow-up		
Study Day	Day -3	Day 1 BL	Day 2	Day 3	Day 4	Day 5	Day 6	Day 7	Day 14 ^e (± 3)	Day 28 (+/- 3)	Day 60 (+/- 7d)
Informed consent	X										
Inclusion/exclusion criteria review	X										
Brief physical exam	X	X		X		X		X	X		
Clinical status using NIAID scale	X	X	X	X	X	X	X	X	X	X	X
Vital signs (BP, RR, HR, Temp)	X	X	X	X	X	X	X	X	X		Xⁱ
O₂ therapy status and SpO₂	X	X	X	X	X	X	X	X	X	X	X
12-lead ECG	X	X^a		X^a		X^a		X^a			Xⁱ
Biomarker plasma samples: MIF, IL-1β, IL-6, TNF-α	X^b	X		X		X		X	X		
PK blood sample^c		X		X		X					
CBC, CMP, CRP, D-dimer, PT, INR	X^d	X		X		X		X	X		Xⁱ
Randomize^f	X										
Administer study drug		X^h	X	X	X	X	X	X			
Adverse event review		X	X	X	X	X	X	X	X	X	X

Prior/Concomitant medication review	X	X	X	X	X	X	X	X	X	X	X
Record survival status ^j									X	X	X

^a 12-lead ECG to be done between 2-4 hours after AM dose.

^b Biomarker blood sample collection at screening is optional if Screening and Day 1 assessments occur on the same day.

^c Collect PK samples on Day 1 in the AM prior to study drug dosing and at 2, 4, 8, and 12 hours (Predose of PM dose); Day 3 and Day 5 prior to AM study drug dosing. PK samples to be collected for 8 subjects only.

^d Serum β-hCG for pre-menopausal women.

^e Telephone follow-up if subject is not in hospital. If subject is no longer hospitalized or cannot return due to COVID restrictions, a telephone follow-up to record O₂ usage/levels, AEs and conmeds may be conducted. All other assessments are optional.

^f Subjects may be randomized during the Screening Phase after all of the screening assessments are completed and subject is considered eligible for the study or on Day 1.

^g If subject prematurely discontinues from the study or is discharged from the hospital on Days 2, 4, or 6 collect biomarker samples in addition to other scheduled assessments. If subject prematurely discontinues from the study or is discharged on Days 1, 3, 5, or 7, conduct the study assessments scheduled on those days.

^h The first dose of study drug may be started in the AM or the PM.

ⁱ Vital signs, ECG and safety labs will be done in intubated subjects only.

^j Survival status is captured on the NIAID questionnaire.

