8 STUDY PARTICIPANTS

8.1 Disposition of Participants and Withdrawals

All participants who provide informed consent will be accounted for in this study. The number of screen failures will be presented. The number and proportion of participants in each analysis set will be presented by treatment arm (in percentage of the number of

Confidential

participants randomly assigned) and overall. The number and proportion of completers will be presented by treatment arm and overall. The number and proportion of early withdrawals will be presented by the coded term for main reason of withdrawal and overall, by treatment arm and overall.

Participants who are in the Safety Analysis Set but not in the Full Analysis Set will be listed. Randomization errors will be listed.

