11 SAFETY AND TOLERABILITY ANALYSIS

All safety analyses will be performed for participants in the safety analysis set.

The analysis of safety assessments in this study will include summaries of the following categories of safety and tolerability data collected for each subject:

- Treatment Emergent Adverse Events:
 - Clinical laboratory Treatment Emergent Adverse Events
 - Discontinuation due to TEAEs
 - Treatment Emergent Serious Adverse Events
- Pregnancies (if any reported)
- Clinical Laboratory Investigations
- Vital Signs
- Physical examinations

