11.1.4 Deaths

If any subject dies during the study, relevant information will be supplied in a data listing, and appropriate SAE narratives.

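### The Safety Analysis Set can omit a dosed subject who has no post-dose safety assessment, and the planned listing of set differences is empty by definition (minor)

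*Combined protocol and SAP*

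**What the plan says.** SAP Section 6 defines two sets that matter here. The Full Analysis Set "will include all randomized subjects", with no further condition. The Safety Analysis Set "will include all randomized subjects who received at least one dose of study drug and had at least one post-dose safety assessment". The SAP does not say what counts as a post-dose safety assessment.

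SAP Section 11 applies the narrower set throughout: "All safety analyses will be performed for participants in the safety analysis set". Section 6.1 adds that subjects in it are analysed by treatment received.

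On accounting for the sets, SAP Section 8.1 plans this listing: "Participants who are in the Safety Analysis Set but not in the Full Analysis Set will be listed". The same section also says "The number and proportion of participants in each analysis set will be presented by treatment arm" and "The number and proportion of early withdrawals will be presented by the coded term for main reason of withdrawal".

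On deaths, SAP Section 11.1.4 says: "If any subject dies during the study, relevant information will be supplied in a data listing, and appropriate SAE narratives". All-cause mortality at Day 28 is a secondary efficacy endpoint (Section 10.2), and efficacy is analysed on the Full Analysis Set (Section 10).

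**The concern.** Membership of the safety set depends on something that happens after exposure. The protocol collects adverse events from the first dose (Section 16.0), and both documents start the treatment-emergent period at the first dose (protocol 19.4, SAP 11.1). Neither rule carries an assessment condition. The set definition therefore allows an exposed subject to be absent from both the numerator and the denominator of the treatment-emergent, serious and discontinuation tables and of the safety-section death table.

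The listing that might be expected to show such subjects looks the wrong way. It asks who is in the safety set but outside the Full Analysis Set, whereas the omitted subject is in the Full Analysis Set and outside the safety set.

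What is at stake is a correct count of exposed subjects and agreement between the two death tables.

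**Working it through.** The plan gives no figure to reproduce on this point, and no power calculation was made. The check is set logic followed by simple proportions.

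**1. Set logic.** Let R = randomized, D = dosed, A = at least one post-dose safety assessment. From SAP Section 6:

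- Full = R
- Safety = R and D and A

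Over the 8 combinations of R, D and A:

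| Difference | Combinations | Who they are |
|---|---|---|
| Safety, not Full (listed in 8.1) | 0 of 8 | nobody, by definition |
| Full, not Safety (not listed) | 3 of 8 | randomized but never dosed (2 combinations), or dosed but not assessed (1) |

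The two groups in the second row differ in kind. A never-dosed subject is properly outside a safety set. A dosed subject is not.

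**2. Can a subject be dosed but not assessed?**

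- After a morning dose on Day 1, the schedule puts an ECG 2 to 4 hours later, which is itself a post-dose safety assessment.
- The Amendment 4 schedule (protocol Table 1, footnote h) also allows an evening start: "The first dose of study drug may be started in the AM or the PM". Day 1 assessments may then all precede the dose.
- Leaving the study or hospital on Day 1 is foreseen (footnote g). Once a subject is out of hospital, footnote e makes the telephone contact permissive and everything else optional.
- The Amendment 2 schedule in SAP 13.1 has no evening-start note, and 31 of the 36 consented subjects came in under that amendment (5 under Amendment 4, SAP 13.2).

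The route exists but is narrow.

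**3. Size.** Assumed arm sizes: 20 (half of the planned 40) and 18 (half of 31 + 5 = 36). The 36 were consented, not necessarily randomized, so 18 is an upper bound for that figure. One subject is 1/20 = 5.0% or 1/18 = 5.6% of an arm.

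One recorded event in the arm, in the omitted subject (exact 95% intervals):

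| Arm size | All dosed subjects | Current definition |
|---|---|---|
| 20 | 1/20 = 5.0% (0.1% to 24.9%) | 0/19 = 0% (0% to 17.6%) |
| 18 | 1/18 = 5.6% (0.1% to 27.3%) | 0/17 = 0% (0% to 19.5%) |

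**4. Direction.** Take an arm of 18 with one omitted subject; the event counts are illustrative.

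- If the omitted subject has one of 3 recorded events, the rate goes from 3/18 = 16.7% to 2/17 = 11.8%, so omission lowers it.
- If the omitted subject has no recorded event and 3 others do, the rate goes from 3/18 = 16.7% to 3/17 = 17.6%, so omission raises it.

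**5. Agreement of the death tables.** Table 14.2.8 is an efficacy table on all randomized subjects. Table 14.3.4.5 is a safety table on the Safety Analysis Set. A death in a dosed but unassessed subject is counted in the first and not in the second.

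**The case against.** A reader might infer that an early death or dropout could pass unseen. The documents do not support that. Section 8.1 gives the size of each set by arm, as a percentage of those randomized, and withdrawals by reason. Listing 16.2.1 covers analysis populations. Section 11.1.4 covers any death with a listing and narrative, survival status is listed (16.2.6.4), and Day 28 mortality is analysed on all randomized subjects.

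A reader might also infer that the exclusion necessarily lowers event rates. It need not. On a natural reading a recorded adverse event or death is itself a post-dose safety assessment, so that subject stays in. A subject with nothing recorded only adds to the denominator.

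The exclusion should also be rare. Adverse event review and vital signs are scheduled on each of Days 1 to 7. Footnote g tells sites to perform the assessments scheduled for Day 1 if the subject leaves that day, and protocol 15.3.4 commits to telephone follow-up of adverse events after discharge in firmer terms than footnote e.

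All of this stands, and it limits the point. It does not remove it:

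- The natural reading is not written down, so the programmer would have to choose it.
- Set counts do not separate never-dosed from dosed-but-unassessed subjects. A reader would have to cross-check the exposure listing (16.2.5).
- The death listing and Day 28 mortality do not return a subject with a non-fatal early event to the treatment-emergent or discontinuation rates.
- The Section 8.1 listing is empty however often the exclusion occurs.

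**Conclusion.** The point holds as a minor defect of definition. The Safety Analysis Set carries an undefined post-dose condition that could drop an exposed subject from every table based on it. The consequences would be an understated number exposed and a possible mismatch between Tables 14.3.4.5 and 14.2.8. Few subjects, quite possibly none, would be affected; each would be about 5% to 6% of an arm, assuming 1:1 allocation and 18 to 20 per arm. No direction of bias can be claimed in advance.

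The empty listing in Section 8.1 is certain and needs no assumption beyond Section 6. The sentence would have made sense under the Full Analysis Set in protocol 19.1, which requires treatment and a post-dose efficacy assessment. The SAP history says that set was corrected in version 2.0, so the sentence may be a leftover; that is an inference.

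**What to change.** - **SAP Section 6:** define the Safety Analysis Set as every subject who received at least one dose of study drug, analysed by treatment received, and delete the post-dose assessment condition.
- **SAP Section 8.1:** list subjects in the Full Analysis Set but not in the safety set, with the reason. The existing listing may stay beside it. Once the safety set no longer requires randomization, it would show anyone dosed without being randomized.

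The cost is a change of SAP wording and one listing, with no new data. The small downside is that a subject with no post-dose data enters the denominator with unknown event status and slightly dilutes the rates. A footnote giving the number of such subjects per arm deals with that.

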6.1 Use of analysis populations in different analyses

Safety analyses will be conducted on the Safety Analysis Set, and participants will be analyzed based on the treatment they received. Efficacy analysis will be conducted on the Full Analysis Set, and participants will be analyzed based on the treatment to which they were randomly assigned.

7 GENERAL ISSUES FOR STATISTICAL ANALYSIS

Data from all clinical assessments will be listed and, where appropriate, summarized by treatment arms using descriptive statistics. Summary (descriptive) statistics of continuous variables include n, mean, standard deviation (SD), median, first quartile (Q1), third quartile (Q3), minimum and maximum values at each time-point. For categorical variables, the number and percent of counts will be presented.

7.1 Definition of Treatment Arms

Treatment arms will be denoted as follows in the TLFs:

- “MN-166” - 50 mg of MN-166 administered orally twice daily
- “Placebo” – Matching Placebo administered orally twice daily

7.2 Definition of Baseline

Unless otherwise specified, baseline is defined as the measurement closest to the date of the first administration of Investigational Medicinal Product (IMP) and preceding the first dose of IMP (MN-166 or Placebo).

7.3 Definition of Visit Windows

The same visit windows will be used as defined in the protocol.

- Screening visit (up to -3 days)
- Day 1 (baseline) (0 days)
- Days 2-7 (0 days)
- Day 14 (± 3 days)
- Day 28 (± 3 days)
- Day 60 (± 7 days)

7.4 Multi-center Study

The study will be conducted at two centers:

Confidential

Denver Health and Hospital Authority

Yale School of Medicine

7.5 Multiple Comparisons and Multiplicity

There are two co-primary endpoints. Because study success requires success on both, each will be tested using a one-sided alpha level value of 0.025 (equivalent to a two-sided alpha of 0.05). All other analyses will be conducted using one-sided tests at the alpha=0.025 level of significance, with no adjustment for multiplicity.

7.6 Planned Subgroup Analyses

No subgroup analyses are planned in this study.

7.7 Analysis Software

All analysis will be performed using SAS® Software version 9.4 or above.

7.8 Clinical Status Scale

In this trial, the National Institute of Allergy and Infectious Diseases (NIAID) 8-point ordinal scale is utilized to assess clinical status at Screening, Days 1-7, and on Days 14, 28, and 60 (for intubated subjects only). In Section 14.5 of the protocol, the numbers (1-8) are in reverse, where a higher number represents improvement, which is inconsistent with the official NIAID 8-point ordinal scale. The SAS programmer will correct the NIAID 8-point ordinal scale to reflect the official scale shown below.

1. Not hospitalized, no limitations on activities
2. Not hospitalized, limitation on activities and/or requiring home oxygen
3. Hospitalized, not requiring supplemental oxygen - no longer requires ongoing medical care
4. Hospitalized, not requiring supplemental oxygen - requiring ongoing medical care (COVID-19 related or otherwise)
5. Hospitalized, requiring supplemental oxygen
6. Hospitalized, on non-invasive ventilation or high flow oxygen devices
7. Hospitalized, on invasive mechanical ventilation or extracorporeal membrane oxygenation (ECMO)
8. Death

8 STUDY PARTICIPANTS

8.1 Disposition of Participants and Withdrawals

All participants who provide informed consent will be accounted for in this study. The number of screen failures will be presented. The number and proportion of participants in each analysis set will be presented by treatment arm (in percentage of the number of

Confidential

participants randomly assigned) and overall. The number and proportion of completers will be presented by treatment arm and overall. The number and proportion of early withdrawals will be presented by the coded term for main reason of withdrawal and overall, by treatment arm and overall.

Participants who are in the Safety Analysis Set but not in the Full Analysis Set will be listed. Randomization errors will be listed.

8.2 Protocol Deviations

The number and proportion of participants with protocol deviations will be presented by treatment arm, for each coded term.

All protocol deviations will be listed.

8.3 Inclusion and Exclusion Criteria

Participants who meet all the inclusion criteria and none of the exclusion criteria are eligible to participate in the clinical trial.

Deviations from inclusion/exclusion criteria will be listed.

9 DEMOGRAPHICS AND OTHER BASELINE CHARACTERISTICS

9.1 Demographics

For variables assumed to be continuous, like age at screening, body weight and height descriptive statistics will be prepared by treatment arm, for each analysis set separately.

For categorical variables like gender, race, ethnicity, frequency tables (n and percentage) will be prepared by treatment arm, for each analysis set separately.

All demography data will be listed.

9.2 Prior and Concomitant Medications

Prior medications/therapies are defined as those for which the end date is prior to the date of first IMP administration. Concomitant medications/therapies are defined as those with start date on or after the date of first IMP administration and those with start date prior to the first IMP use but with end date on or after the date of first IMP administration.

Concomitant medications in the database will be coded using the most recent version of the World Health Organization Drug Dictionary which employs the Anatomical Therapeutic Chemical (ATC) classification system. The number and percentage of participants who took prior and concomitant medications will be summarized separately by ATC classification first level (alphabetically), ATC classification second level (in decreasing order of frequency) and treatment arm.

Confidential

These therapeutics will be listed by subject along with their classification, indication of the treatment, total daily dose and start and stop date of the treatment.

The number and percentage of participants who took prior and concomitant treatments will be presented separately.

All prior and concomitant medication data will be listed.

9.3 Baseline and Screening Conditions

Baseline and Screening condition data will be assessed by treatment arm using descriptive statistics. No inferential test statistics are planned for baseline comparison of the treatment arms.

9.3.1 Baseline Medical History

All medical history records will be coded according to the latest version od MedDRA and summarized by system organ class and preferred term. The number and percentage of participants in different medical history categories will be presented by treatment arm.

10 EFFICACY ANALYSIS

Efficacy analysis will be performed on the Full Analysis Set. All efficacy measurements will be listed.

10.1 Primary Efficacy Variable Analysis

The co-primary efficacy endpoints are listed below. The primary analysis for each of these two endpoints will be conducted using Pearson's chi-square tests. Because study success is defined as success on both, each of the two co-primary endpoints will be tested using a one-sided significance level of 0.025.

- Proportion of subjects free from respiratory failure
 - Calculate the proportion of the subjects free from supplemental oxygen (invasive mechanical ventilation, non-invasive ventilation, high-flow oxygen, ECMO, CPAP, BiPAP, nasal cannula) at Day 7
- Proportion of subjects with improvement in clinical status using the NIAID 8-point ordinal scale and discharge record at Day 7
 - Calculate the proportion of the subjects who improved at least one-point from baseline

For each of the two co-primary endpoints, subjects whose response status is unknown will be assumed to be nonresponders.

A supportive analysis for each of the two co-primary endpoints will be conducted using the Mantel-Haenszel test stratified by the randomization stratification variable (use of IL-6 antibody therapy).

Confidential

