12.0 SELECTION OF SUBJECTS

12.1 Study Population

This study will enroll approximately 40 subjects diagnosed with COVID-19 who are at risk for developing acute respiratory distress syndrome (ARDS) receiving standard of care including anticoagulation. Randomization of subjects will be stratified by use of IL-6 antibody therapy.

Subjects who do not meet all of the inclusion criteria or who meet any of the exclusion criteria are not eligible to participate in the study.

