12.2 Inclusion Criteria

1. Written or verbal informed consent by subject or subject representative is obtained
2. Male or female subjects age 18 to 80 years, inclusive
3. SARS-CoV-2 infection confirmed with WHO criteria (including a positive PCR of any specimen, e.g., blood, respiratory, stool, urine, or any other body fluid)
4. Chest imaging (radiograph, CT scan or lung ultrasound) with abnormalities consistent with COVID-19 pneumonia
5. SpO₂ ≤ 92% on room air (RA), RR ≥ 24 breaths per min on RA, and/or requirement for supplemental oxygen
6. At least 1 risk factor which may put patient at higher risk for more severe illness from COVID-19: Age > 65, underlying serious heart disease, chronic lung disease, moderate to severe asthma, body mass index of ≥ 40 or diabetes
7. C-reactive protein > 35 mg/L
8. No known allergies to the study drug or its excipients

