12.3 Exclusion Criteria

1. Suspected active bacterial, fungal, viral, or other cause of respiratory failure other than COVID-19
2. Known or suspected immunosuppression with immunosuppressant medications or chemotherapeutic agents
3. Active primary lung cancer or another metastatic malignancy to the lungs
4. Moderate to severe liver failure (see [section 12.4](#)) defined by Child-Pugh score of ≥ 7 measured by:
 - Total bilirubin
 - Serum albumin
 - INR
 - Ascites
 - Hepatic encephalopathy
5. The following abnormal laboratory tests if any of the criteria are met:
 - a. Platelet Count < 75,000 /mm³
 - b. White Blood Count < 2500 /mm³
 - c. ALT or AST or Total Bilirubin > 3 x ULN
 - d. Bilirubin > 3 mg/dL
 - e. Serum albumin less than 28 g/L
6. Subject is on dialysis
7. On home ventilator support or continuous domiciliary O₂ therapy for baseline lung disease
8. Active tuberculosis (TB) infection
9. Lactating or pregnant at Screening

10. History of stomach or intestinal surgery or any other condition that could interfere with or is judged by the Investigator to interfere with absorption, distribution, metabolism, or excretion of study drug
11. Treatment with an investigational drug or off-label medication within 5 half-lives or 30 days whichever is longer prior to study drug treatment
12. Participating in another COVID-19 clinical trial
13. Any other serious medical condition or abnormality that, in the Investigator's opinion, would preclude participation in the study.

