15.2 Randomization

Once all of the screening assessments have been conducted, subject will be randomized. Randomization will be stratified according to subject's use of IL-6 antibody therapy and may occur on either the last day of screening or the morning of Day 1.

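### No planned analysis of the oxygen-free co-primary uses baseline respiratory support, and the IL-6 randomisation factor enters only a supportive test

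*Combined protocol and SAP*

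**What the plan says.** **Tests.** SAP section 10.1: "The primary analysis for each of these two endpoints will be conducted using Pearson's chi-square tests". It then adds: "A supportive analysis for each of the two co-primary endpoints will be conducted using the Mantel-Haenszel test stratified by the randomization stratification variable", the variable being IL-6 antibody use. Each co-primary is tested at one-sided 0.025 and both must succeed (SAP 7.5).

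**Endpoints.** The first co-primary is absolute status at Day 7: "Calculate the proportion of the subjects free from supplemental oxygen". The second is improvement of at least one point from baseline on the NIAID scale.

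**Randomisation.** Protocol 12.1: "Randomization of subjects will be stratified by use of IL-6 antibody therapy". Protocol 15.2 repeats the factor. Baseline oxygen support is not a stratification factor.

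**Who can enter.** Inclusion criterion 5 offers alternatives, low saturation or a raised respiratory rate on room air, the latter ending "breaths per min on RA, and/or requirement for supplemental oxygen". Protocol 15.3.3 provides extra Day 60 assessments for subjects intubated at screening or later.

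**What is collected and used.** Oxygen therapy status and NIAID status are recorded at Screening and Day 1 (protocol Table 1). SAP 7.6 plans no subgroup analyses. In SAP 10.2, change-from-baseline endpoints get an ANCOVA with treatment and the endpoint's own baseline value, without the IL-6 factor; secondary proportions get Pearson tests. SAP 7 and 9.3 provide for descriptive summaries by arm, and SAP 13.3 lists a table of baseline disease characteristics. None of these names oxygen support.

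**The concern.** A subject who enters on room air needs only to stay off oxygen to count as a success on the first co-primary. A subject who enters ventilated must come off all support within a week. Baseline support is therefore likely to be a strong predictor of this endpoint, and nothing in the design balances it between arms.

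If the arms differ by chance, the Day 7 comparison mixes that difference with the drug effect. The distortion can go either way: it can suggest an effect that is absent or hide one that is present. No planned analysis of this endpoint separates the two. The SAP is also uneven here, since it adjusts each change endpoint for its own baseline but not this co-primary. SAP section 5 says the results will be used to design later studies, so a distorted estimate would carry forward.

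The IL-6 factor raises a smaller point. Randomisation is stratified by it, but the deciding test and the ANCOVAs ignore it.

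**Working it through.** **Inputs from the documents.** One-sided alpha 0.025, which SAP 7.5 equates to two-sided 0.05; both give a critical value of 1.960, so that statement is correct. Allocation is 1:1. Consented: 31 + 5 = 36 (SAP 13.1 and 13.2), which may include screen failures. The SAP states no response rates, oxygen mix or power, so there is no planned figure to reproduce.

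**Assumptions.** 18 per arm; 10 of 36 on room air at baseline; with no drug effect, probability of being oxygen-free at Day 7 is 0.8 from room air and 0.3 from oxygen.

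**Step 1: bias from a 7 v 3 split.** Expected successes with no drug effect:
- MN-166: 7 × 0.8 + 11 × 0.3 = 8.9 of 18
- Placebo: 3 × 0.8 + 15 × 0.3 = 6.9 of 18
- Apparent difference: 2.0/18 = 0.111, which equals (7 − 3)/18 × (0.8 − 0.3)

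**Step 2: how often.** The room-air count in one arm is hypergeometric (36 subjects, 10 on room air, 18 drawn). P(7 or more on MN-166) = 0.13; 0.26 in either direction.

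**Step 3: conditional levels.** Exact enumeration of all outcomes, rejecting when z > 1.960, without continuity correction:
- Pearson: z = (p1 − p0)/√(2p̄(1 − p̄)/n)
- Mantel-Haenszel (MH) over strata s: z = Σ(a_s − n1_s·m_s/t_s)/√Σ[n1_s·n0_s·m_s(t_s − m_s)/(t_s²(t_s − 1))], where a_s is successes on MN-166, m_s all successes, n1_s and n0_s the arm sizes, and t_s the stratum size

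| Room air, MN-166 v placebo | Pearson level |
|---|---|
| 3 v 7 | 0.0025 |
| 5 v 5 | 0.0185 |
| 7 v 3 | 0.0921 |

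MH by oxygen status stays at 0.022 to 0.025 across these splits. At a common odds ratio of 6, Pearson power is 0.40 at 3 v 7 and 0.82 at 7 v 3; MH power is 0.61 to 0.63.

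**Step 4: other assumptions.** Pearson level:
- Null rates 0.7/0.4: 0.067 at 7 v 3 and 0.010 at 3 v 7
- Null rates 0.6/0.4: 0.054 and 0.016
- 17, 19 or 20 per arm (0.8/0.3, 7 v 3): 0.085, 0.080, 0.065
- 4 on room air, split 3 v 1: 0.048; 14 on room air, split 9 v 5: 0.089

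**Step 5: two categories or three.** Assume null rates 0.9 (room air), 0.5 (supplemental oxygen) and 0.1 (ventilated), 18 per arm, room air balanced at 5 v 5 and ventilated 2 v 6, hence 11 v 7 on supplemental oxygen. By simulation, MH on an on/off split rejects in 6.7% of trials and MH on three categories in 2.5%. An on/off split is too coarse if ventilated subjects are enrolled.

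**Step 6: trial level.** Averaged over splits, the Pearson level on this endpoint is 0.032. It is 0.0317 with no strata at all, so the excess over 0.025 comes from discreteness, not oxygen. Requiring both co-primaries, and over assumed patterns of improvement on the second, the joint rate is 0.005 to 0.023 averaged over splits and 0.009 to 0.065 at 7 v 3. It reaches 0.032 and 0.092 only if the two endpoints agree in every subject.

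**Step 7: IL-6 factor.** N = 36, balanced strata, 2 to 9 users per arm, odds ratio 6. Mean power of MH minus Pearson, in percentage points, by the gap in null response between strata:

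| Gap (points) | Mean difference |
|---|---|
| 0 | −0.8 |
| 10 | −0.6 |
| 20 | 0.0 |
| 30 | +1.1 |
| 50 | +5.6 |

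**The case against.** - **The Pearson test is valid.** This stands. Randomisation protects the level on average, and the error shown is conditional on an imbalance. A reader might infer that the trial's false-positive rate is inflated; Step 6 does not support that, and SAP 7.5 requires success on both endpoints.
- **The figures rest on assumed rates and counts.** This stands. With 0.6/0.4 the level at 7 v 3 falls to 0.054. The direction holds whenever baseline support predicts the outcome; the size is unknown.
- **Baseline oxygen will be visible anyway.** Largely so. SAP 7 and 9.3 cover baseline summaries by arm, and oxygen assessments have their own listing. A reader might infer that an imbalance would go unseen, which is too strong. Seeing it is not adjusting for it, however, and an adjustment chosen after unblinding would count as unplanned under SAP 2.2.3.
- **Other analyses partly encode oxygen support.** The second co-primary is defined from baseline, and the Day 7 NIAID ANCOVA uses baseline NIAID. True, but neither analyses the oxygen endpoint.
- **The IL-6 change is a preference.** Mostly right. A reader might infer that demoting the stratified test costs power or makes the primary test invalid. Neither follows: ignoring a balanced prognostic stratum makes Pearson conservative, and MH shows no average power gain until the gap reaches about 30 points. The stratified result will be reported in any case. Exclusion criterion 2 ("Known or suspected immunosuppression with immunosuppressant medications or chemotherapeutic agents") may also leave the stratum small.
- **This is a proof-of-concept study without a sample-size calculation.** True, but the SAP sets a formal success rule for it.

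**Conclusion.** The point holds for the oxygen-free co-primary. Its definition ignores the starting state, entry allows starting states from room air to intubation, and no planned analysis of it uses the baseline support already collected. Under 0.8/0.3 null rates with 10 room-air subjects and 18 per arm, a split at least as uneven as 7–3 favours MN-166 with probability 0.13; at 7 v 3 the one-sided level is 0.092 instead of 0.025. The opposite split, 3 v 7, cuts power at odds ratio 6 to 0.40. Stratifying by baseline support removes most of this dependence on the split.

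The conclusion is limited to conditional error on one co-primary under assumed rates. It does not make the Pearson test invalid. The IL-6 part is a matter of matching the analysis to the randomisation and ranks lower.

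**What to change.** Before unblinding:

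1. **Add an adjusted analysis of the oxygen-free co-primary.** Pre-specify a Mantel-Haenszel analysis stratified by last pre-dose respiratory support in three categories: no supplemental oxygen; supplemental oxygen; non-invasive ventilation or high-flow oxygen, invasive ventilation or ECMO. SAP 7.2 already supplies the timing rule ("baseline is defined as the measurement closest to the date of the first administration", and before the first dose). State a rule for merging sparse categories, based on counts pooled over arms. Report the result beside the Pearson test and say in advance how a disagreement will be read.
2. **Name this variable** in the by-arm baseline summary that SAP 7, 9.3 and 13.3 already broadly cover.
3. **Lower priority.** Consider making the planned Mantel-Haenszel test by IL-6 antibody use primary for both co-primaries, with Pearson supportive and a collapsing rule for a nearly empty stratum. Add the factor to the SAP 10.2 ANCOVAs.

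**Cost.** Items 1 and 2 need SAP wording and a few program lines, use data already collected, and change no decision rule. The deciding test therefore stays open to imbalance; what is gained is a pre-specified check on it. Item 3 does change the primary test. If the factor is not prognostic it loses about 0.8 points of power on average at N = 36 (at most 3.8 in the cases run). In the ANCOVAs it costs one degree of freedom, moving the two-sided 5% t value from 2.035 to 2.037.
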